6.1 Anticipated Toxicities

A list of the adverse events and potential risks associated with the agents administered in this study appear below and will determine whether dose delays and modifications will be made or whether the event requires expedited reporting **in addition** to routine reporting.

Risk has been assessed based on nonclinical toxicological studies and clinical experience of in-class compounds, along with preliminary data from the ongoing single-agent FTIH studies with GSK1120212 and GSK2141795. Procedures to minimize or monitor potential risks are listed below.

6.1.1 Predicted Overlapping Toxicities

Gastrointestinal (GI) Toxicity: Interim medical history, continuous assessment of AEs, physical examination, and clinical laboratory assessments will be used to identify and assess toxicity in the GI tract. Supportive therapy will be provided according to standard medical practice. Treatment will be discontinued for clinically significant toxicity.

Rash: Subjects will be followed closely for signs and symptoms of rash and aggressive supportive care is recommended. Guidelines for rash prophylaxis and for rash treatment management have been provided in Section 6.3.1 (table titled "Dose Modification Guidelines and Management for Rash"). Treatment will be dose reduced or discontinued for clinically significant toxicity not adequately controlled by supportive care measures.

6.1.2 GSK2141795 Safety Profile and Management

Based on available adverse event (AE) data from 151 subjects dosed as of the data cut-off date of May 6, 2012, the most common toxicities of GSK2141795 monotherapy or in combination with trametinib are gastrointestinal (GI)-related (diarrhea, nausea, and vomiting) and fatigue (Investigator's Brochure, 2012). Hyperglycemia, hypoglycemia, mucositis, and rash are also commonly observed. In addition, three cases of hypothyroidism have been noted.

Interim medical history, continuous assessment of AEs, physical examination, and clinical laboratory assessments will be used to identify and assess toxicity in the GI tract. Supportive therapy will be provided according to standard medical practice. Treatment will be discontinued for clinically significant toxicity.

Diarrhea: This is the most frequent drug-related AE in participants receiving GSK2141795. Most diarrhea events reported were Grade 1 and 2. Based on current data, the majority of cases of diarrhea occur within the first 3 to 4 weeks of starting the drug. In most cases, diarrhea resolves with interruption of GSK2141795 dosing and implementation of supportive treatment. Based on preliminary data, re-challenge with a reduced dose of GSK2141795 is tolerated. Early diarrhea management for subjects taking GSK2141795 is critical and must be initiated as soon as the first episode of diarrhea has occurred. Supportive care interventions should include dietary modifications, anti-diarrheal medications, and supplementary intravenous hydration as needed.

Mucosal Inflammation: Mucositis has been observed as a dose-limiting toxicity (DLT).

Early intervention for signs and symptoms of mucosal inflammation is recommended and encouraged. Based on preliminary data, dose interruption followed by dose reduction on re-challenge can ameliorate symptoms. Supportive care interventions should include good oral hygiene, adequate pain control, prevention of superinfection, and maintenance of adequate of hydration with supplementary intravenous hydration as needed. **Rash**: Rash may or may not be associated with pruritus. Preliminary data suggest that drug interruption and dose reduction upon re-challenge ameliorate the symptoms. Rash management should focus on symptom relief and maintenance of an intact integument. Dermatology consult is recommended when clinically appropriate. Topical steroid creams have been found to provide some relief from symptoms. Treatment will be dose reduced or discontinued for clinically significant toxicity not adequately controlled by supportive care measures.

Hyperglycemia: Hyperglycemia occurred in participants receiving \geq 75 mg/day with the majority of events occurring at doses exceeding the maximum tolerated dose (MTD) of 75 mg/day. Treatment-related grade 3 or grade 4 events were observed at 75 mg, 100 mg, and 150 mg daily doses. The frequency and severity of hyperglycemia AEs is reduced at the 75mg/day dose as compared with higher doses. It is not clear if oral anti-hyperglycemic drugs are useful to ameliorate the hyperglycemia, although both intravenous and sliding scale insulin have been helpful.

To reduce the risk of hyperglycemia, participants with abnormal fasting glucose values at screening will be excluded. In addition, participants with Type 1 diabetes will also be excluded; however, participants with Type 2 diabetes will be allowed if diagnosed ≥ 6 months prior to enrollment, and if presenting with regular hemoglobin A1C (HbA1C) $\leq 8\%$ at screening. Participants will have glucose and insulin monitored during the study. If hyperglycemia is observed, supportive therapy will be provided according to standard medical practice. Treatment will be dose reduced or discontinued for clinically significant toxicity that cannot be adequately managed medically.

Hypoglycemia: Asymptomatic hypoglycemia occurred in participants receiving \geq 75 mg/day. Treatment-related grade 3 or grade 4 events were observed at 75 mg and 100 mg daily doses. The mechanism of hypoglycemia is currently unknown. Careful monitoring of glucose levels and encouragement of adequate oral intake are recommended.

Thyroid Events: Reversible minimal to mild hypertrophy of follicular cells was seen in the thyroid glands of dogs given 5 mg/kg/day for 4 weeks. The relationship to GSK2141795 and clinical significance are unknown, although three cases of drug-related hypothyroidism have been reported. Continued monitoring for thyroid function (thyroid-stimulating hormone laboratory testing) will be incorporated in all clinical protocols. Supportive therapy will be provided according to standard medical practice, and treatment will be discontinued if necessary.

Other Glandular Events: In both rats and dogs, several glandular structures (salivary, nasal, mammary, and Brunner's glands) had reversible reductions in secretory content and/or apoptosis of individual acinar cells. The mechanism for this finding is not understood, although it may result in dry mouth, a toxicity that has been reported in some participants. Frequent monitoring with medical history, physical examination, and clinical laboratory assessments will be done. If clinically significant toxicity is observed,

supportive therapy will be provided according to standard medical practice, and treatment will be discontinued if necessary.

6.1.3 Other Toxicities Based on Clinical Experience

Ocular Events (GSK1120212): To reduce the risk of ocular toxicity, subjects with a history of retinal vein occlusion (RVO) or central serous retinopathy (CSR), predisposing factors for RVO or CSR, or predisposing retinal pathology as described by ophthalmologic exams will be excluded. Ophthalmologic exams will be performed at baseline and as clinically warranted. Aggressive management and evaluation of all ocular symptoms, as well as specific ocular toxicity stopping criteria, will be implemented.

Metabolic Toxicity: To reduce the risk of hyperglycemia, subjects with abnormal fasting glucose values at screening will be excluded. In addition, subjects with Type 1 diabetes will also be excluded; however subjects with Type 2 diabetes will be permitted in Part 2 of the study only if they meet the specified entry criterion. If hyperglycemia is observed, supportive therapy will be provided according to standard medical practice. Treatment will be dose reduced or discontinued for clinically significant toxicity that cannot be adequately managed medically.

Cardiac toxicity (GSK1120212): To monitor cardiac function, echocardiogram (ECHO) exams and electrocardiograms (ECGs) will be performed at baseline, regular intervals, and as clinically warranted during study treatment. Specific cardiac toxicity stopping criteria will be implemented and treatment will be discontinued for clinically significant toxicity.

6.1.4 Other Potential Toxicities Based on Nonclinical Data

Hematologic Toxicity: Complete blood counts (CBC) will be measured frequently during therapy to monitor for hematologic toxicity. Supportive therapy will be provided according to standard medical practice and treatment will be discontinued for clinically significant toxicity.

Glandular Abnormalities: Frequent monitoring with medical history, physical examination and clinical laboratory assessments. If clinically significant toxicity is observed, supportive therapy will be provided according to standard medical practice and treatment will be discontinued if necessary.

Thyroid Abnormalities: Thyroid stimulating hormone (TSH) will be measured frequently during therapy to monitor for thyroid dysfunction. Supportive therapy will be provided according to standard medical practice and treatment will be discontinued for clinically significant toxicity.

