There are 3 clinical studies for GSK2141795. PCS112689 is a first-time-in-human (FTIH), dose-escalation study in subjects with cancer to characterize the safety, pharmacokinetic, and pharmacodynamic profiles of GSK2141795. Enrollment is complete as the primary objective was met and 2 subjects remain on study as of the data cut-off date. PCS113124 is an open-label, multiple-dose, dose-escalation study designed to explore the potential dose response relationship between the pharmacokinetics of GSK2141795 and [¹⁸F] FDG PET pharmacodynamic markers of glucose metabolism in tumor tissue. The study enrolled a total of 12 subjects in order to meet the study's primary objective without necessitating enrolment of the estimated maximum number of subjects. PCS113124 is clinically complete and the clinical study report is in progress. TAC113886 is an ongoing dose-escalation, open-label study to determine the recommended Phase II dose and regimen for the combination of the orally administered MEK inhibitor GSK1120212 and the orally administered AKT kinase inhibitor GSK2141795.

Single-dose (Day 1) PK parameters of GSK2141795 were evaluated in the first-time-inhuman (FTIH) study (PCS112689). Preliminary data indicated that plasma concentrations for GSK2141795 were measurable for all subjects over the 72 hours after a single dose over the dose range tested (10 mg to 150 mg). In addition, drug concentrations were measurable on Day 8, suggesting that GSK2141795 can still be found in the plasma at least 1 week after a single dose of study drug over the dose range tested (75 mg to 100 mg). While the exposures for the 100 mg and 150 mg doses were similar following a single dose, drug exposure following multiple doses was approximately in proportion to dose. GSK2141795 accumulated 2.5- to 8.4-fold with repeat daily dosing. Mean area under the concentration-time curve (AUC₍₀₋₂₄₎) and maximum plasma concentration (C_{max}) values generally increased in a dose-proportional manner, although there was variability among subjects. Median time to reach peak concentration (T_{max}) across doses was 3 hours and ranged from 0 to 4 hours. The mean value for the effective half-life of elimination ($t_{1/2}$, eff) across subjects was 3.0 days and ranged from approximately 1.3 to 5.5 days.

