9. STUDY CALENDAR

Baseline evaluations should be conducted within 14 days prior to start of protocol therapy. Scans must be done ≤ 28 days prior to the start of therapy. All assessments must be performed prior to administration of any study medication. All study assessments should be administered within +/-3 days of the protocol-specified date, unless otherwise noted. Study assessments not required after an indicated timepoint should be performed as clinically indicated in the future. In the event that the participant's condition is deteriorating, laboratory evaluations should be repeated within 48 hours prior to initiation of the next cycle of therapy. One treatment cycle is 28 days in duration.

Study Assessments ^a	Screen ^b	Cycle 1				Cycle 2	Cycle 3	Cycle 4	Subsequent Cycles ^c	Even Cycles	Off-Treatment
		Day 1	Day 8	Day 15	Day 22	Day 1	Day 1	Day 1	Day 1	Between Days 22 - 28	Visit ^d
Informed Consent	Х										
Demographics	Х										
Medical History / Interim History	х	х	X e	х	X e	х	х	х	х		х
Physical Exam ^f	Х	Х		Х		Х	Х	Х	Х		Х
ECOG Performance Status	х	X ^g		х		х	х	х	х		х
Vital Signs ^w	Х	Х		Х		Х	Х	Х	Х		Х
Height and Weight ^v	Х	X g				Х	Х	Х	Х		Х
Hematology ^h	Х	X g	X e	Х	X e	Х	Х	Х	Х		Х
Clinical Chemistry ⁱ	Х	X g	X e	Х	X e	Х	Х	Х	х		Х
Fasting Blood Glucose ^v	Х	Х	Х	Х	Х	Х	Х	Х	Х		Х
Coagulation ^j	Х	X g									
Creatinine Clearance	Х										
Pregnancy Test ^k	Х							Χv			х
Fasting Lipid Panel	Х							Χv			Х
Hemoglobin A1C	Х							Χv			Х
TSH	Х							Χv			Х
1,5-anhydroglucitol (1,5-AG) ¹	х			х		XI	XI	X ¹			
12-Lead ECG ^m	Х	Х		Х					Х		Х
ECHO or MUGA ⁿ	Х					X ^u					Х

Study Assessments ^a	Screen ^b	Cycle 1			Cycle 2	Cycle 3	Cycle 4	Subsequent Cycles ^c	Even Cycles	Off-Treatment	
		Day 1	Day 8	Day 15	Day 22	Day 1	Day 1	Day 1	Day 1	Between Days 22 - 28	Visit ^d
Ophthalmic Exam °	Х										
Disease Assessment ^r	Х									Х	Х
Brain Imaging ^s	Х									Х	
Chest Imaging (X-ray or CT) ^t	х									х	х
Trametinib and GSK2141795 Dosing		Х (Continuo	us daily d	osing)					Х	
Circulating Free Tumor DNA ^p		X ^g									х
Archival Tumor Tissue ^p	Х										
Biopsies ^q	Х		Х								Х
Concomitant Medications	х	х	(Continu	ous)							х
Adverse Events		Х	(Continu	ous)							X

a. Assessments should be done prior to administration of study drug(s), unless otherwise specified.

b. Within 14 days before first dose with the following exceptions:

- LVEF assessment can occur within 45 days of first dose
- disease assessment can occur within 28 days of first dose

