11. ADVERSE EVENT REPORTING REQUIREMENTS

11.1 Definitions

11.1.1 Adverse Event (AE)

An adverse event (AE) is any undesirable sign, symptom or medical condition or experience that develops or worsens in severity after starting the first dose of study treatment or any procedure specified in the protocol, even if the event is not considered to be related to the study.

Abnormal laboratory values or diagnostic test results constitute adverse events only if they induce clinical signs or symptoms or require treatment or further diagnostic tests.

Please see Section 6.1, "Anticipated Toxicities" for specific information about expected toxicities for both study agents.

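### TSH is promised frequently during therapy, but the calendar schedules no on-drug TSH in the first 12 weeks

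*Combined protocol and SAP*

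**What the plan says.** Two places in the safety text commit to thyroid monitoring. Section 6.1.4 says: "Thyroid stimulating hormone (TSH) will be measured frequently during therapy to monitor for thyroid dysfunction". Section 6.1.2, under thyroid events, says: "Continued monitoring for thyroid function (thyroid-stimulating hormone laboratory testing) will be incorporated in all clinical protocols". The reason is given in Section 6.1.2: among the 151 subjects dosed with GSK2141795 by the May 2012 cut-off, "three cases of hypothyroidism have been noted", and the thyroid paragraph calls these cases drug-related. It also reports mild thyroid changes in dogs dosed for 4 weeks.

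The schedule is in Section 9. The TSH row has three marks: screening, Cycle 4 Day 1 and the off-treatment visit, which falls about three weeks after the last dose. Footnote i lists the clinical chemistry analytes, and TSH is not among them. Beyond the scheduled tests, Section 9 allows discretionary ones: "Study assessments not required after an indicated timepoint should be performed as clinically indicated in the future".

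**The concern.** The text promises frequent measurement on treatment, yet the calendar gives no on-treatment measurement for 12 weeks. The word has no stated interval, but Section 6.1.4 uses the same wording for blood counts, and there the calendar does deliver frequent draws.

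At stake is whether a thyroid change is picked up while the participant is still on drug, which is when both thyroid paragraphs contemplate supportive care or stopping treatment. In the first 12 weeks detection depends on symptoms. That route is weaker than usual here, because the most common toxicities of GSK2141795, alone or with trametinib, "are gastrointestinal (GI)-related (diarrhea, nausea, and vomiting) and fatigue". Fatigue is also a common symptom of low thyroid function, so it may be put down to the study drugs without a TSH being ordered.

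**Working it through.** The plan gives no figure on this point, so there is none to reproduce. The check has three steps.

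**1. Timing and count of draws (Section 9).** Cycles last 28 days, so Cycle 4 Day 1 is study day 3 × 28 + 1 = 85, which is 84/7 = 12 weeks after the first dose.

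| Test | Scheduled draws, Cycle 1 Day 1 through Cycle 4 Day 1 | Number |
|---|---|---|
| Hematology | Cycle 1 Days 1, 8, 15, 22; Day 1 of Cycles 2, 3, 4 | 7 |
| TSH | Cycle 4 Day 1 | 1 |

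Both are described in Section 6.1.4 as frequent.

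**2. Share who stop before week 12.** No discontinuation rate is given, so assumptions are needed.
- Time to progression is exponential, with 6-month PFS, S6, between 15% and 50%. Section 2.1.2 gives 25% for bevacizumab, which lies inside this range.
- Progression ends treatment at the scan that shows it. Footnote r of Section 9 puts scans on Days 22 to 28 of even cycles. The first is therefore due by day 56. The second falls on days 106 to 112, after Cycle 4 Day 1. Under this assumption only progression found at the first scan removes a participant before day 85.

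Share progressed by day 56 = 1 − exp(−h × 56/30.44), where h = −ln(S6)/6 per month.

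| S6 | h per month | Share by day 56 | Of 35 |
|---|---|---|---|
| 0.15 | 0.316 | 44% | 15.4 |
| 0.25 | 0.231 | 35% | 12.1 |
| 0.50 | 0.116 | 19% | 6.7 |

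Stops for toxicity, withdrawal or clinical deterioration are not counted.

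**3. Thyroid cases in that group.** The phase I rate is 3/151 = 2.0% (exact 95% CI 0.4% to 5.7%). Applied to 35 participants, it gives 35 × 3/151 = 0.70 expected cases (0.14 to 1.99). Multiplying by the shares above gives 0.70 × 0.19 = 0.13 to 0.70 × 0.44 = 0.31 cases among participants with no scheduled on-drug TSH. This takes the pooled rate at face value and treats events as independent of stopping time.

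**After the fix.** A TSH on Cycle 2 Day 1 (study day 29) comes before the first scan. Under the same assumption, everyone who stops at that scan would already have one on-drug TSH. Those who leave during Cycle 1 would still have none; Section 10.1.1 foresees progression or death that early.

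**The case against.** The strongest reply is that the calendar is the operative schedule and looks deliberate. Pregnancy test, fasting lipids, HbA1c and TSH share the same three marks, which reads as a planned 12-week safety block. Section 6.1 contains carried-over text (6.1.3 mentions a Part 2 that this trial does not have), so the adverb may carry little intent. The commitment in 6.1.2 is to include TSH testing, and the calendar does that. Interim history is taken weekly in Cycle 1 and on Day 1 of each later cycle, so symptoms will be heard. No dosing rule uses a TSH threshold, and Section 11.1.1 says abnormal laboratory values "constitute adverse events only if they induce clinical signs or symptoms or require treatment or further diagnostic tests".

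Much of this stands, and it limits the weight of the point. It does not supply an on-drug measurement in the first 12 weeks, which the safety text leads a reader to expect.

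The size estimate is also open to challenge. The documents give neither the onset times nor the doses of the three cases. The phase I experience went up to 150 mg, against 50 mg here. Early stoppers also have shorter exposure. Nothing shows that the first 12 weeks are the period of risk, or that a day-29 test would have found those cases.

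Two stronger readings are tempting. One is that no TSH follows Cycle 4, because the footnote letter on that mark leads to a note about height. The lettering there is visibly disordered and may come from the PDF conversion, so this cannot be relied on. The other is that the off-treatment draw is uninformative because the effective half-life of GSK2141795 "across subjects was 3.0 days and ranged from approximately 1.3 to 5.5 days". That describes drug clearance. The documents say nothing about how fast TSH recovers.

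**Conclusion.** The mismatch between Section 6.1.4 and Section 9 is real and minor. It does not depend on how the Cycle 4 mark is read: even a repeat every 12 weeks from that visit leaves the first 12 weeks uncovered.

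The number without an on-drug TSH rests on the assumed PFS range and the week-8 stopping rule. The expected number of thyroid cases among them is well below one at the observed phase I rate. A reader might infer that up to 44% of participants would have thyroid toxicity missed. The documents do not support that, because the percentage counts people without a scheduled test, nearly all of whom would be expected to have no thyroid event. Each early stopper is also still due a TSH at the off-treatment visit. The response-rate analysis, its error rates and the sample size are untouched.

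**What to change.** In the Section 9 calendar, mark TSH at Cycle 2 Day 1, and optionally at Cycle 3 Day 1. Keep the existing tests at screening, Cycle 4 Day 1 and the off-treatment visit. Hematology and clinical chemistry are already drawn at both added visits, so TSH can be run on the same blood.

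The cost is at most 35 extra assays for Cycle 2 alone, or 2 × 35 = 70 for both cycles, and fewer as participants come off treatment. No visit or procedure is added. The first scheduled on-drug TSH moves from week 12 to week 4.

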6.1.5 Adverse Events List for GSK1120212

The most commonly reported AE's in Phase I studies of GSK1120212 are listed below. Other SAE's that attributed to GSK1120212 but less common include: hepatic encephalopathy, chorioterinopathy, pneumatosis intestinalis, retinal hemorrhage, myopathy and pulmonary hypertension.

Most Commonly Reported Adverse Events for trametinib (GSK1120212)		
in Phase I Studies		
rash	dyspnea	
diarrhea	pyrexia	
nausea	pneumonia	
fatigue	febrile neutropenia	
vomiting	AST increased	
anemia	ALT increased	
peripheral edema	dry skin	
abdominal pain	thrombocytopenia	
constipation	peripheral edema	
dermatitis acneiform	cough	
decreased appetite	chills	
pruritus		

6.1.6 Adverse Events List for GSK 2141795

The most commonly reported adverse events in Phase I studies of GSK2141795 are listed below.

Most Commonly Reported Adverse Events for GSK2141795		
fatigue	pyrexia	
nausea	back pain	
diarrhea	mucositis	
decreased appetite	hypoglycemia	
blood glucose increased/hyperglycemia	hypertension	
vomiting	liver enzyme elevation	
dyspnea	dehydration	
constipation	pruritus	
rash	edema	
cough		

6.2 Toxicity Management

The following section outlines specific management guidelines for the following toxicities: overdose (6.2.1), rash (6.2.2), diarrhea (6.2.3), hypertension (6.2.4), and other toxicities in 6.2.5 including QTc alterations, hypocalcemia and hypercalcemia,

pneumonitis, left ventricular changes, liver chemistry changes, visual changes, and all other toxicities.

6.2.1 Overdose

There is no specific guidance available regarding overdose due to the lack of clinical experience. In case of an acute overdose, it is recommended that activated charcoal be administered orally to reduce the absorption of GSK1120212 and GSK2141795.

